10.0 Statistical Considerations

Sample size justification.

The purpose of this trial is to assess feasibility of a cluster-randomized, cluster-crossover design. To assess whether compliance can be maintained after cross-over events, we will need to observe two cross-over events to each mode while maintaining an equal number of treatment blocks for each mode. Doing so will require a total of 9 months. Based on the experience of a prior trial in the same ICU,⁷⁰ we anticipate an average of 75 patients on mechanical ventilation will be enrolled per month. In 9 months, we expect to enroll 675 patients, of whom 69 will be enrolled during washout periods and excluded from the primary analysis. The resulting 606 patients will be included in the primary analysis.

While the sample size was determined to demonstrate feasibility of the cluster-crossover design, we anticipate this pilot will be the largest randomized trial of ventilator modes to date, and as such, we plan to compare ventilator free days to day 28 (primary outcome) between groups. In a prior cluster-randomized cluster-crossover trial in the same ICU,⁷⁰ mechanically ventilated patients experienced a median of 22 VFDs [IQR 0-25 VFDs] and an intra-cluster intra-period correlation of 0.01. With 606 (202 in each group) patients in the primary analysis, a standard deviation in the primary outcome of VFDs of 11 days, and a two-sided alpha of 0.05, the MODE trial will have 80 percent statistical power to detect an absolute difference between groups in the sole primary clinical endpoint of Ventilator Free Days of 3 days.

Primary Analysis of the Primary Clinical Outcome

The sole pre-specified primary outcome of ventilator free days will be compared between the three trial groups in an intention-to-treat fashion among all patients enrolled in the trial except those admitted during one of the 3-day washout periods. To estimate the conditional effect of a group assignment on an individual patient given the values of the covariates for that patient, we will use a proportional odds model with independent covariates of group assignment (volume control, pressure control, or adaptive

pressure control) and time. Time (in days) will be treated as a continuous variable with values ranging from 1 (first day of enrollment) to 272 (final day of enrollment) and will be analyzed using restricted cubic splines with multiple knots to allow for non-linearity resulting from seasonality or secular trends. In addition to assessing for an overall group effect within the model, we will estimate the differences between each pair of modes by extracting 95% confidence intervals from the model.

Sensitivity Analyses of the Primary Clinical Outcomes:

We will repeat the primary clinical outcome analysis with adjustment for pre-specified baseline covariates.

We will repeat the analyses of the primary outcome and feasibility outcomes among all patients enrolled in the trial including those initiated on invasive mechanical ventilation in the study ICU during one of the pre-specified 3-day washout periods.

Analysis of Effect Modification for the Primary Outcomes.

We will examine whether pre-specified baseline variables modify the effect of study group on the primary clinical outcome using formal tests of statistical interaction in a proportional odds model. Independent variables will include study group assignment, the potential effect modifier of interest, and the interaction between the two (e.g., study group * history of COPD) and time. Significance will be determined by the P value for the interaction term, with values less than 0.10 considered to suggest a potential interaction and values less than 0.05 considered to confirm an interaction.

We will examine whether the following baseline variables modify the effect of study group on the primary outcome:

- Age (continuous variable);
- Duration of invasive mechanical ventilation prior to enrollment (0 minutes; 1 to 360 minutes; >360 minutes);
- Pre-enrollment fraction of inspired oxygen (FiO₂)(continuous variable);
- SOFA score at enrollment (continuous variable);
- Shock receiving vasopressors (yes, no)
- Indication for intubation (categories are not mutually exclusive)
 - Hypoxemic respiratory failure (yes, no);
 - Hypercarbic respiratory failure (yes, no);
 - Altered mental status or airway protection (yes, no);
- Chronic Obstructive Pulmonary Disease (yes, no);

Analysis of the Exploratory, Feasibility, and Clinical Outcomes

Each of the exploratory outcomes will be compared between groups in an intention-to-treat fashion in the primary analysis population. Continuous outcomes will be compared between groups in a similar manner as the primary clinical outcome. A logistic model will be used for binary outcomes, a multinomial model for categorical outcomes, and a proportional odds model for ordinal and continuous outcomes.

Corrections for multiple testing

We have pre-specified a single primary clinical outcome, which will have a test of statistical significance for difference between groups. Consistent with recommendations of the Food and Drug Administration and the European Medicines Association, the clinical outcome will be tested using a two-sided p-value with a significance level of 0.05. For all other analyses, emphasis will be placed on the estimate of effect size with 95% confidence intervals, as recommended by the International Committee of Medical Journal Editors, and no corrections for multiple comparisons will be performed.

Handling of missing data

The primary outcome is not anticipated to be missing for any patients. Missing data will not be imputed for the primary outcome or any secondary or exploratory outcomes. In adjusted analyses, missing data for covariates will be imputed using multiple imputations.

Interim Analysis

In addition to ongoing monitoring of safety throughout the trial, we will plan for the DSMB to conduct a single interim analysis for safety after the ICU has been assigned to each of the three study modes, that is, after enrollment of patients for 3 months. At the interim analysis, the DSMB will evaluate the incidence of the following outcomes across the study groups (volume control, pressure control, or adaptive pressure control):

- Pneumomediastinum or pneumothorax during the course of mechanical ventilation,
- Episodes of hypoxemia while receiving invasive mechanical ventilation: SpO₂ < 85% for more than 5 minutes,
- In-hospital mortality to study day 28.

The stopping boundary for safety will be met if the P value for the difference between groups is 0.016 or less, which is an a priori threshold determined by adjusting the p-value threshold of 0.05 for multiple comparisons by dividing 0.05 by the 3 outcomes. The DSMB will consider whether it is necessary to stop the trial or whether randomization to any one study group should be stopped, while the other two groups continue enrolling patients. Given the design of the study is to demonstrate feasibility and pilot trial procedures rather than demonstrating efficacy, there will be no stopping boundary for efficacy or futility.

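### The stated 80% power for a 3-day difference shows no allowance for the intra-period correlation quoted beside it; allowing for it gives about 57% to 79%, depending on an unstated between-period correlation

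*Combined protocol and SAP*

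**What the plan says.** Section 10.0 (sample size justification) sets the nine-month duration by the number of crossovers needed to judge feasibility, and then adds a power statement for VFDs. From an earlier cluster-crossover trial in the same ICU it quotes the median VFDs "and an intra-cluster intra-period correlation of 0.01". The next sentence gives three inputs. The number analysed comes as "With 606 (202 in each group) patients in the primary analysis". For the spread it uses "a standard deviation in the primary outcome of VFDs of 11 days". The significance level is "a two-sided alpha of 0.05". It concludes that "the MODE trial will have 80 percent statistical power to detect an absolute difference between groups in the sole primary clinical endpoint"; the size of that difference is put at 3 days. It gives no design effect, effective sample size or between-period correlation.

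Section 6.5 assigns the whole ICU to one mode for each one-month block. Section 4.0 confirms a single ICU. The primary analysis is a proportional odds model with group and a spline in time, which assesses an overall group effect and gives pairwise confidence intervals. On testing, the plan says: "We have pre-specified a single primary clinical outcome, which will have a test of statistical significance for difference between groups".

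**The concern.** Patients treated in the same ICU-month share one assignment and whatever else was particular to that month. If outcomes vary from month to month beyond chance, a comparison of modes is less precise than one between individually randomised patients. The plan quotes a correlation that bears on this, but its power figure can be obtained without using it.

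What is at stake is how the clinical comparison is read. A reader told that power is 80% for 3 days will take a null result as fairly strong evidence against an effect of that size. Section 2.0 presents the pilot as the step before a large trial, so the figure may also be taken at face value by whoever designs that trial.

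**Working it through.** **Inputs (section 10.0 unless noted).** n = 202 per group; SD = 11 days; difference = 3 days; two-sided alpha 0.05 (z = 1.96); z for 80% power = 0.8416; within-period correlation 0.01; nine one-month blocks, three per mode. Analysed patients per block: m = 606/9 = 67.3. Not given: the between-period correlation. It is written below as a share c of 0.01, with c assumed to lie between 0 and 1.

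**Reproducing the plan's figure, patients independent.**
- SE = 11 × √(2/202) = 1.0945 days
- 3/1.0945 = 2.741; power = Φ(2.741 − 1.96) = 78.3%
- Detectable difference at 80% power = (1.96 + 0.8416) × 1.0945 = 3.07 days

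This matches the stated 80% and 3 days to rounding.

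**Applying the correlation.** For a crossover within one ICU, the design effect is DE = 1 + (m − 1) × 0.01 − m × 0.01 × c. The last term removes the correlation that is common to all months and so cancels from the mode comparison. The SE is multiplied by √DE.

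| Share c between periods (assumed) | DE | SE (days) | 3/SE | Pairwise power | Detectable difference (days) |
|---|---|---|---|---|---|
| 0 | 1.663 | 1.412 | 2.125 | 56.6% | 3.95 |
| 0.5 | 1.327 | 1.261 | 2.380 | 66.3% | 3.53 |
| 0.8 | 1.125 | 1.161 | 2.585 | 73.4% | 3.25 |
| 1.0 | 0.990 | 1.089 | 2.755 | 78.7% | 3.05 |

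For example, at c = 0: DE = 1 + 66.3 × 0.01 = 1.663, effective n = 202/1.663 = 121.4 per group, and power = Φ(2.125 − 1.96) = 56.6%.

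**Overall three-group test (2 df, mean scale).** The noncentrality is 202 × S/(121 × DE), where S is the sum of squared deviations of the three group means. If one mode differs by 3 days from the other two, S = 1 + 1 + 4 = 6. If the third mode lies midway, S = 2.25 + 0 + 2.25 = 4.5.

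| | Independent | DE 1.663 |
|---|---|---|
| One mode differs by 3 days | noncentrality 10.02, power 81.6% | noncentrality 6.02, power 58.6% |
| Third mode midway | noncentrality 7.51, power 68.8% | noncentrality 4.52, power 46.2% |

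**The case against.** A reader might infer that power is 57% on the plan's own figures. The documents do not support that. The 57% needs a between-period correlation of zero, or a reading of the 0.01 as purely month-to-month correlation within the ICU. The second reading is natural if the value was estimated from that one ICU, but the text does not say so.

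A reader might also infer that the correlation was never applied. That cannot be shown either. If the within- and between-period correlations were taken as equal, power would be 78.7%, as consistent with the stated 80% as the 78.3% for independent patients. What can be said is that no allowance is visible.

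It is also tempting to say that the plan powered the wrong test. This is secondary. The text refers only to a difference between groups, and for independent patients the overall test has 81.6% power if one mode differs, so 80% lies between the two readings. The ambiguity is still worth removing, because the midway pattern gives less.

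All these figures compare means, while the planned model is proportional odds. An illustrative calculation with an assumed zero-inflated VFD distribution gives about 89% power for independent patients and about 70% at design effect 1.66, before any loss from the time spline. The documents do not give that distribution, so this cannot replace the range, but it shows that the mean scale may understate power. In the other direction, a test on 6 between-block degrees of freedom would have about 43% power at c = 0, but no such test is planned. Whether the planned model's standard errors reflect ICU-month correlation at all is a separate question about the analysis.

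Finally, the sample size was set for feasibility, and the plan commits to pairwise confidence intervals, so interpretation need not rest on power. That stands, and it limits the severity.

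**Conclusion.** The concern holds as one about an unsupported figure. The stated 80% is what independent patients would give, to rounding, and the documents show no allowance for assignment by ICU-month. With the quoted 0.01 applied, pairwise power for 3 days is about 57% to 79%, and the difference detectable with 80% power is about 4.0 to 3.1 days. These figures assume SD 11, equal blocks of about 67 patients, a normal critical value and a comparison of means.

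The position within the range depends on a correlation that the documents do not give. The top requires no month-to-month variation. The plan itself expects some: section 6.5 uses permuted blocks to limit seasonal effects, and section 10.0 fits a spline for seasonality and secular trends. The top is therefore the least plausible point, but the documents do not fix any other.

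This is a should-fix. It corrects a number that the plan chose to state, but it does not undermine the reason for the sample size.

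**What to change.** Keep enrolment, duration and the feasibility justification. Restate the power sentence so that it gives the within-period correlation, the assumed between-period correlation and the resulting design effect. The between-period value could be sought from the data of the earlier trial in the same ICU. Until it is known, wording such as this would do:

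*With 606 patients in nine one-month blocks, SD 11 days, two-sided alpha 0.05 and a within-period correlation of 0.01, power for a 3-day difference between two modes is about 57% if none of that correlation is shared between periods (design effect 1.66) and about 79% if all of it is (design effect 0.99). The difference detectable with 80% power is about 4.0 to 3.1 days.*

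Say whether the figure refers to a pairwise comparison or to the overall three-group test, and add the latter's power: at design effect 1.66, about 59% if one mode differs by 3 days and 46% if the third lies midway. Note that these are mean-scale approximations to the planned proportional odds model.

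The cost is one paragraph and a less favourable stated power. No patients are added.

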- **The intervention is delivered by unit-level protocols.** Mechanical ventilator settings and titrations are performed by respiratory therapists using unit-level protocols. In this cluster-randomized trial, the entire unit will be assigned to the same mode of mechanical ventilation for each 1-month block. Obtaining informed consent from every eligible patient in the ICU prior to emergency tracheal intubation and initiation of mechanical ventilation would be impracticable.

Because the study involves minimal risk, the study would not adversely affect the welfare or privacy rights of the participant, and obtaining informed consent would be impracticable, we will request a waiver of informed consent. Numerous previous randomized trials comparing two standards of care for interventions such as emergency intubation and methods of respiratory support during critical illness have been completed with waiver of informed consent.^{39–47}

6.5 Randomization:

During each one-month block of the study, the ICU will be assigned to either volume control, pressure control, or adaptive pressure control. The order of the study group assignments will be generated by computerized randomization using permuted blocks of 3 to minimize the impact of seasonal variation. The last 3 days of each block will be a washout period during which the ICU will continue to use the assigned mode, but new patients will not be included in the primary analysis. The 3-day washout period will limit the number of patients who experience a ‘crossover’ from one assigned mode to another while receiving a mandatory mode of mechanical ventilation.

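### The stated 80% power fits a model without time adjustment; the planned calendar-time spline lowers it, slightly with 3 knots and substantially with 4 or 5, and the knots are not specified

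*Combined protocol and SAP*

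**What the plan says.** The combined protocol and SAP gives its power statement in section 10.0, under the sample size justification. The inputs are 606 patients in the primary analysis (202 per mode), "a standard deviation in the primary outcome of VFDs of 11 days", and a two-sided test at the 5% level. The paragraph concludes that "the MODE trial will have 80 percent statistical power to detect an absolute difference between groups"; the size of that difference is 3 ventilator-free days. It names no formula and mentions no allowance for time. It also reports "an intra-cluster intra-period correlation of 0.01" from a prior trial in the same ICU.

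The primary analysis in the same section is a proportional odds model with group and calendar day (1 to 272). Day "will be analyzed using restricted cubic splines with multiple knots to allow for non-linearity resulting from seasonality or secular trends". The number and location of knots are not given. The model yields an overall group effect and pairwise differences with 95% confidence intervals. Under the multiple-testing paragraph, the single planned significance test is the between-group test of the primary outcome.

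Section 6.5 assigns the whole ICU to one mode per month, in an order "generated by computerized randomization using permuted blocks of 3 to minimize the impact of seasonal variation". Patients enrolled in a washout at the end of each month (3 days) are left out of the primary analysis.

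**The concern.** In an individually randomised trial, adjusting for calendar time costs almost nothing, because treatment is nearly unrelated to date. Here one ICU uses one mode at a time, so mode is fully determined by calendar day and takes only nine monthly steps. A restricted cubic spline with k knots uses k-1 degrees of freedom. Together with the intercept and two mode terms, the model takes 5, 6 or 7 of the nine monthly means for k = 3, 4 or 5. The spline therefore competes with mode for the same between-month information.

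If the power figure ignores this, it does not describe the planned model, and a null result would be read against a sensitivity that the analysis may not have. The size of the gap depends on a setting the plan leaves open and on which mode order was drawn.

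**Working it through.** **1. Reproduce the stated figure.** Inputs from section 10.0: n = 202 per group, SD 11, difference 3 days, two-sided alpha 0.05.

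- Two groups, unadjusted: SE = 11 × √(2/202) = 1.0945. Power = Φ(3/1.0945 − 1.96) = Φ(0.781) = 78.3%. The difference detectable with 80% power is (1.96 + 0.84) × 1.0945 ≈ 3.07 days.
- Three groups, unadjusted F test, means (0, 0, 3): noncentrality = 202 × (1 + 1 + 4)/121 = 10.02 on 2 and 603 df, giving 81.4%.

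Either agrees with 80% to rounding. Neither contains time.

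**2. Add the planned spline.** Further inputs: nine months over days 1-272, last 3 days of each month dropped, and permuted blocks of 3, hence 6³ = 216 equally likely sequences. Assumptions: even enrollment over the remaining days, intra-cluster correlation 0, and 3, 4 or 5 knots at standard quantiles of day.

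For each sequence, the intercept and spline are projected out of the mode indicators. The variance inflation factor (VIF) of a pairwise contrast is its variance with the spline divided by its variance without. Pairwise power = Φ(3/(1.0945 × √VIF) − 1.96). Overall power comes from the noncentral F distribution with one mode 3 days different, averaged over which mode that is.

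| Time term | Overall test: mean (lowest) | Pairwise: mean (range) | VIF: mean (maximum) |
|---|---|---|---|
| None | 81.4% | 78.3% | 1.00 |
| 3 knots | 78% (70%) | 75% (64-78%) | 1.10 (1.40) |
| 4 knots | 68% (34%) | 64% (14-77%) | 1.56 (10.0) |
| 5 knots | 62% (31%) | 57% (16-77%) | 1.81 (8.0) |

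The lowest overall values are over sequences and over which mode differs; the pairwise ranges are over sequences and pairs. Mean power is the average of the powers, not the power at the mean VIF. At the mean VIF, the pairwise difference detectable with 80% power is 3.07 × √VIF = 3.2, 3.8 and 4.1 days. Calendar-length months and other knot placements change the mean powers by no more than about 1.5 points.

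**3. Proportional-odds scale.** The planned model is ordinal, so the absolute level depends on the outcome distribution, which must be assumed. For assumed distributions close to the quoted median of 22 and IQR of 0-25, a proportional-odds shift worth 3 days has unadjusted pairwise power of about 85-91%. Allowing for the spline gives about 82-89%, 70-76% and 63-69% with 3, 4 and 5 knots.

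**4. What the spline buys.** Assume an annual cycle of 3 days peak to trough (the documents give no figure), no true mode effect, and any starting phase. A model with the three-month randomisation set as a factor has VIF 1.00, but can leave bias of just over 1 day in a pairwise contrast. Its overall test has a false-positive rate of about 7.5% on average and 12-13% at worst, the same as with no time adjustment. With 3 knots the worst case is about 9%; with 4 or 5 knots the rate stays at 5%.

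**The case against.** The best defence has four parts.

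- **The planned test is the overall one.** A reader might take the pairwise 75%, 64% and 57% as the power of the primary analysis. The documents do not support that: pairwise contrasts get confidence intervals only. For the overall test the loss is smaller, and with 3 knots the average is within about 2 points of the stated 80%.
- **The model is ordinal, not linear.** With 3 knots, power on the proportional-odds scale may be at or above 80%. This stands. It does not rescue 4 or 5 knots.
- **The knot number is an assumption.** This stands too. The larger losses are conditional on 4 or 5 knots, and the averages conceal a wide range by sequence. But the setting is open only because the plan leaves it open.
- **The trial is a feasibility pilot.** Section 10.0 sets its size by the number of crossovers needed, not by the 80%. A reader might infer that the trial is too small or needs more patients; that does not follow. What remains is an explicit power statement and a test at the 0.05 level that would be read together.

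Two further inferences go too far. One is that the authors used a two-sample t-test: no formula is named, and the unadjusted F test fits about as well. The other is that the spline is a mistake because permuted blocks already balance season. They balance it between three-month sets, but not within a set for the one sequence drawn, and step 4 shows that a set factor does not remove that trend.

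**Conclusion.** The point holds as a mismatch between the power statement and the planned model. The 80% is reproduced only without time. Under the planned spline, average power of the overall test on the plan's own scale falls to about 78%, 68% or 62% with 3, 4 or 5 knots. The drop is slight at 3 knots and material at 4 or 5, where an unlucky sequence could bring power near one third. These figures rest on assumed knots, even enrollment, SD 11 and a zero intra-cluster correlation. The quoted correlation of 0.01 is a separate matter and is not counted here. The finding concerns how the clinical comparison is described and read; it does not show that the spline is the wrong adjustment or that the trial is wrongly sized.

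**What to change.** Keep the restricted cubic spline as the primary time adjustment. State the number and location of knots in section 10.0 before the outcome is analysed by group. The choice is a trade: fewer knots keep more power, while more knots give better protection against seasonal and secular trend.

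Replace the 80% sentence with the power, or the detectable difference, for the overall group test under that spline and the mode sequence actually drawn, and give the expected precision of each pairwise contrast. Compute these from the design inputs, not from observed outcomes, and state whether the figure is on the linear or the proportional-odds scale.

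A model with the three-month randomisation set as a factor may be added as a sensitivity analysis. It should not replace the spline, because it leaves trend within a set unadjusted.

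The cost is a few sentences and one recalculation, with no extra patients or data. The downside is that the stated power will probably look less favourable.

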Exploratory Outcomes	Feasibility Outcomes 
 Exposure to assigned study mode in first 3 days: Proportion of time in the assigned mode while receiving invasive mechanical ventilation in the study ICU between enrollment and 72 hours after enrollment

	
 • Adherence to study mode in first 3 days: Proportion of time in the assigned mode while receiving invasive mechanical ventilation in the study ICU with a mandatory mode between enrollment and 72 hours after enrollment (excluding time spent in spontaneous modes) • Time from enrollment to initiation of assigned mode of mechanical ventilation • Receipt of a “Mode Modification Sheet” completed by treating clinicians 
Exploratory Efficacy and Safety Outcomes
 
 • Median exhaled tidal volume (mL/kg predicted body weight) on each study day • Exhaled tidal volumes above target range: Proportion of recorded breaths with exhaled tidal volume values above the target range ($>8\text{mL/kg}$ predicted body weight) on each study day • Hypoxemia during mechanical ventilation: Episodes of hypoxemia during mechanical ventilation: $\text{SpO}_2 < 85\%$ for more than 5 minutes • Severe acidemia during mechanical ventilation: Episodes of severe acidemia during mechanical ventilation: $\text{pH} < 7.1$ on blood gas • Number of blood gas laboratory tests per day while receiving mechanical ventilation • Pneumomediastinum or pneumothorax during course of mechanical ventilation • SOFA score daily on the first 7 study days • Delirium and coma-free days to day 28 
Exploratory Clinical Outcomes:
 
 • ICU-free days to study day 28 • Hospital-free days to study day 28 • In-hospital mortality to study day 28
Analysis	The primary analysis of the primary outcome (ventilator-free days) will be conducted in an intention-to-treat fashion using a proportional odds model with independent covariates of group assignment (volume control, pressure control, or adaptive pressure control) and time since beginning enrollment (in days).
Sample Size	The trial will be conducted for a total of 9 months as this is the duration needed to evaluate the feasibility of the cluster-randomized multiple-crossover design. Based on data from a prior trial in the same ICU, we expect to enroll 675 patients, of whom 69 will be enrolled during washout periods and 606 patients will be included in the primary analysis.

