Enrollment (Day 0): date and time of clinical events (hospital admission, ICU admission, intubation); source of admission to study ICU; age; sex; race; ethnicity; height, weight;⁶⁴ SOFA score;⁶⁵ Glasgow Coma Scale score;⁶⁶ Elixhauser Comorbidity Index;⁶⁷ history of present illness; vital signs (temperature, heart rate, systolic blood pressure, diastolic blood pressure, SpO₂); mechanical ventilator settings (mode, set and exhaled tidal volumes, set and actual respiratory rate, minute ventilation, set and total positive end-expiratory pressure, peak pressure, plateau pressure, inspiratory time, flow pattern, FiO₂); serum laboratory values (white blood cell count, hemoglobin, platelet count, sodium, potassium, bicarbonate, creatinine, bilirubin, alanine aminotransferase, aspartate aminotransferase, lactate, arterial and venous pH, PaCO₂, PaO₂, SaO₂).

Daily On-Study (Days 0-28): Vital signs, ventilator settings, screening for and performance of spontaneous awakening trials and spontaneous breathing trials, and serum laboratory values (as above); Mean daily dose of sedative infusions (propofol, dexmedetomidine, morphine, fentanyl, and midazolam); CAM status; RASS score; Daily completion of each element from ICU Liberation Bundle (A-F); Beginning and end time of Spontaneous Breathing Trials; vasopressor and inotrope infusions (norepinephrine, epinephrine, vasopressin, phenylephrine, dobutamine, angiotensin-2, dopamine); “Mode Modification Sheet” (use, time, reason); Characteristics of treating clinicians (respiratory therapist, attending, pulmonary fellow, registered nurse) providing direct care; Use of therapies for refractory hypoxemia (prone positioning, ECMO, neuromuscular blockade, inhaled pulmonary dilators); SOFA score; ARDS criteria by the Berlin Definition;⁶⁸ Stage II or greater AKI by KDIGO criteria;⁶⁹ cardiac arrest, pneumothorax or pneumomediastinum.

Termination (Days 0-28): Vital status at 28 days; time of liberation from invasive mechanical ventilation; receipt and duration of vasopressors; receipt and duration of renal replacement therapy; tracheostomy; duration of ICU and hospital admission.

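### The primary model for ventilator-free days adjusts for calendar time but for no patient characteristic; a short, named set of baseline covariates should move from the sensitivity analysis into the primary model

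*Combined protocol and SAP*

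**What the plan says.** Section 10.0 introduces the primary model with this aim: "To estimate the conditional effect of a group assignment on an individual patient given the values of the covariates for that patient". Its terms are group and time; the Trial Summary gives "independent covariates of group assignment (volume control, pressure control, or adaptive pressure control) and time since beginning enrollment (in days". Time runs from day 1 to day 272 and is "analyzed using restricted cubic splines with multiple knots to allow for non-linearity resulting from seasonality or secular trends".

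Patient-level adjustment comes later in the same section, as a sensitivity analysis: "We will repeat the primary clinical outcome analysis with adjustment for pre-specified baseline covariates". The covariates are not listed at that point. The missing-data paragraph adds: "In adjusted analyses, missing data for covariates will be imputed using multiple imputations".

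The Day 0 extraction list in section 7.5 includes "source of admission to study ICU; age; sex; race; ethnicity; height, weight", and also SOFA, Glasgow Coma Scale, the Elixhauser index, vital signs, ventilator settings and laboratory values. Section 10.0 defines nine baseline variables as effect modifiers, among them "SOFA score at enrollment (continuous variable". They enter interaction models one at a time.

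Section 6.5 randomizes the order of modes in permuted blocks of 3 to limit seasonal effects. There are nine one-month periods, three per mode.

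**The concern.** Randomization by month balances case mix over nine units, not over about 600 patients. If one month happens to bring sicker patients and the next does not, the difference falls on whichever modes were assigned. A smooth function of calendar day cannot follow such jumps. A model that holds age and severity of illness can remove the part that those variables measure.

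The wording of the target also sits awkwardly with the model, because odds ratios are non-collapsible. Leaving out a prognostic covariate pulls the odds ratio toward 1, even under perfect balance. The planned model therefore estimates something closer to a population-average odds ratio than to the effect for a patient with given characteristics.

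This matters because VFDs carry a formal two-sided 0.05 test, a power statement and a directional hypothesis (section 3.2), even though the trial is a pilot.

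**Working it through.** **1. The plan's own figure.** Section 10.0 gives 202 per group, SD 11, a 3-day difference, two-sided alpha 0.05 and 80% power.

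SE = 11 × √(2/202) = 1.095. 3/1.095 = 2.741. Power = Φ(2.741 − 1.960) = 0.783.

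The figure reproduces to within two points. It uses neither covariate adjustment nor the quoted intra-period correlation of 0.01.

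**2. The same approximation with adjustment.** The residual SD is 11 × √(1 − R²). R² is assumed. The last column also applies a design effect of 1 + (606/9 − 1) × 0.01 = 1.66. That assumes no between-period correlation and that the covariates explain the same share of variance within and between months.

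| Assumed R² | Power for 3 days | Detectable difference at 80% (days) | Power with the 0.01 correlation |
|---|---|---|---|
| 0 | 0.783 | 3.07 | 0.566 |
| 0.05 | 0.803 | 2.99 | 0.587 |
| 0.10 | 0.824 | 2.91 | 0.610 |
| 0.20 | 0.865 | 2.74 | 0.661 |
| 0.30 | 0.906 | 2.57 | 0.719 |

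**3. The model the plan uses.** Step 2 is a linear-model result, so a proportional odds model was simulated. Each of 2,000 runs had nine months of 67 patients, permuted blocks of 3, a 3-df time spline and one standardized prognostic covariate. The outcome had eight ordered categories, with about 35% in the lowest (assumed). One mode differed from the other two by a conditional log odds ratio of 0.5. Latent R² is g²/(g² + π²/3), with covariate coefficient g of 0.6, 0.8 and 1.0. Power is for the overall test of group, so it is not comparable with step 1.

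| Latent R² | Power, unadjusted | Power, adjusted | Mean log OR (model SE), unadjusted | Mean log OR (model SE), adjusted |
|---|---|---|---|---|
| 0.10 | 0.65 | 0.70 | 0.47 (0.217) | 0.51 (0.219) |
| 0.16 | 0.60 | 0.69 | 0.44 (0.217) | 0.49 (0.221) |
| 0.23 | 0.56 | 0.70 | 0.42 (0.214) | 0.51 (0.220) |

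The standard error does not fall. Power rises because the estimate is less attenuated: at R² 0.16 the ratio of estimate to SE goes from 0.44/0.217 = 2.03 to 0.49/0.221 = 2.22.

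**4. Abrupt differences between months.** The same simulation was run with no mode effect, latent R² 0.16, and an assumed between-month correlation of the covariate. The table shows the type I error of the overall test at nominal 0.05.

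| Covariate correlation within month | Group + spline | Also adjusted |
|---|---|---|
| 0 | 0.053 | 0.057 |
| 0.01 | 0.068 | 0.051 |
| 0.03 | 0.108 | 0.047 |
| 0.05 | 0.140 | 0.049 |

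The simulation error near 0.05 is √(0.05 × 0.95/2000) ≈ 0.005. A separate rank-based simulation (3,000 runs, R² 0.16) agreed: 0.052, 0.068, 0.106 and 0.137 with the spline alone, and 0.048 to 0.052 adjusted. In both, the measured covariate was the only source of month-to-month variation. This is the case most favorable to adjustment.

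**The case against.** The strongest reply is that the adjusted analysis is already planned, so the point is about order, and that an unadjusted primary comparison in a randomized pilot is legitimate. Both statements are true. A reader might infer that the primary analysis is invalid or unprotected against time. The documents do not support that: permuted blocks and a flexible spline are real protection against seasonal and secular change. What they leave open is abrupt variation between months.

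Other tempting readings also go too far.

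- **A contradiction in the estimand.** Enrollment day is formally a covariate with a value for each patient, and the sentence goes on to name group and time as its covariates. The wording and the model fit poorly, but they do not flatly conflict.
- **Lost precision, counted in patients.** The factor 1/(1 − R²) belongs to linear models. Step 3 shows no smaller standard error, so a saving in patients should not be claimed for this model.
- **A trial short of its stated power.** The stated figure reproduces on the plan's own inputs. A material shortfall appears only when the 0.01 correlation is applied, which is a separate question.
- **Covariates never specified.** The text supplied does not list them, but the version history mentions alignment with a statistical analysis plan, which may do so.
- **All candidates ready to use.** The Day 0 list names neither COPD nor indication for intubation, and vasopressor infusions appear under daily data. Enrollment coincides with ventilation in the study ICU, and the list gives no time window, so some values may postdate the assigned mode. The plan itself expects missing covariates.

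The pilot argument limits the weight of the point but does not remove it, given the formal test. A pilot should also rehearse the analysis that the larger trial will need.

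**Conclusion.** The point holds as a recommended improvement, not as a defect that invalidates the analysis. The primary model contains no patient characteristic, although prognostic data are collected, and with three months per mode it leaves abrupt case-mix differences in the comparison.

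The size is conditional on assumptions. On the plan's approximation, adjustment adds about 2 to 12 power points for R² of 0.05 to 0.30 (0.803 − 0.783 to 0.906 − 0.783). In the proportional odds simulation it adds about 5 to 14 points (0.70 − 0.65 to 0.70 − 0.56). The type I error result depends on an assumed clustering of case mix by month: at 0.01 the inflation is small (0.068), and at 0.05 it is large (0.140). The documents give neither R² nor that clustering.

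Adjustment corrects only for what is measured. Residual within-month correlation needs its own allowance.

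**What to change.** Make the primary model group, the time spline and a short named set of baseline covariates. The set should hold at least age and enrollment SOFA, with values recorded before or at enrollment and the window stated. Add pre-enrollment FiO₂, vasopressor receipt, prior ventilation, COPD or indication only where a value from before the assigned mode is available. Use the multiple imputation already planned for missing covariates. Report the group-plus-time model as the sensitivity analysis. Fix the list before outcomes are analyzed by group.

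If the present order is kept, the sentence describing the target should be reworded to say that the effect is conditional on calendar time only.

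For age and SOFA the cost is a change to the analysis text and a defined time window, with no new data collection. The downsides are that the odds ratio becomes conditional on the chosen covariates, so it must be reported as such, and that some covariate values will be imputed in the primary analysis.
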